4.3 Subject Recruitment and Screening

Potential subjects will be identified in the Duke post-COVID clinic by clinical staff at their standard of care (SOC) at 6-12 wks. after their initial COVID-19 diagnosis. The clinical staff will focus on identifying subjects with persistent and continued dyspnea after COVID-19 infection. At initial SOC visit (post-diagnosis of COVID positive), subjects will undergo evaluation in pulmonary clinic. Pulmonary function testing (PFTs) 6-minute walk test (6MWT), and relevant labs will be ordered as indicated by the pulmonary physician. Subjects will be invited to participate in the post-COVID Pulmonary Biorepository and the COVID Long-Haulers pilot study. A subject can enroll in the COVID Long Haulers pilot without enrollment in the Biorepository.

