^{129}Xe MRI metrics will include RBC/barrier, barrier/gas, RBC/gas, and several spectroscopic indices. Continuous data will be presented using the mean \pm SD if normally distributed and median with 25th and 75th percentiles otherwise. We are fortunate to be able to compare the findings in our images to a database of approximately 30 healthy reference subjects whom we have scanned to date. These subjects have undergone the same ^{129}Xe MRI protocol and were recruited with no histories of smoking or cardiopulmonary disease, FEV1>80%, FEV1/FVC>0.70 and DLCO >80%. For subjects to be included in the reference cohort they further had a ventilation defect percentage \leq 6%, (upper limit of normal VDP (Ebner '19)) as well as RBC/barrier \geq 0.45 (at TR=15 ms), and image SNR>5, based on the Rose criterion. Comparisons between these groups will use analysis of variance (ANOVA) methods or Kruskal-Wallis test as appropriate.

8 Safety and Adverse Events

8.1 *Overview*

As the sponsor of the study, Duke University Medical Center and the Principal Investigator shall be solely responsible for complying, within the required timelines, any safety reporting obligation to competent Health Authorities, IRB and any participating (co or sub) investigators, as defined in applicable laws and regulations. For this protocol, safety data include adverse events and special situations, including pregnancies.

8.2 *Management of Safety data*

This study has been designated as an interventional study. As such, all adverse events, special situations including pregnancies and product quality complaints will be reported as described in this protocol from the time a subject has signed and dated an Informed Consent Form (ICF) until 30 days after the last documented use of the study drugs (i.e., end of study (9 months)).

Adverse Event

An **adverse event** (AE) is any symptom, sign, illness, or experience that develops or worsens in severity during the study. Intercurrent diseases or injuries should be regarded as adverse events. Abnormal results of diagnostic procedures are considered to be adverse events if the abnormality:

CONFIDENTIAL

This document is confidential and the property of the Duke University.

- results in study withdrawal
- is associated with a serious adverse event
- is associated with clinical signs or symptoms
- is associated with Abnormal lab values
- leads to additional treatment or to further diagnostic tests

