- is considered by the investigator to be of clinical significance

Serious Adverse Event

Adverse events are classified as serious or non-serious. A ***serious adverse event*** is any AE, that is:

- fatal
- life-threatening
- requires or prolongs hospital stay
- results in persistent or significant disability or incapacity
- a congenital anomaly or birth defect
- an important medical event

Important medical events may not be immediately life-threatening but are clearly of major clinical significance. They may jeopardize the subject and may require intervention to prevent one of the other serious outcomes noted above. For example, drug overdose or abuse, a seizure that did not result in an in-patient hospitalization, or intensive treatment of bronchospasm in an emergency department would typically be considered serious.

All adverse events that do not meet any of the criteria for serious should be regarded as ***non serious adverse events***.

NOTE: DEATH FOR ANY REASON WILL BE REPORTED AS A SERIOUS ADVERSE EVENT.

Post-study Adverse Event

The investigator should follow all unresolved adverse events until the events are resolved, the subject is lost to follow-up, or the adverse event is otherwise explained. At the last scheduled visit, the investigator should instruct each subject to report any subsequent event(s) that the resident, or the subject's physician, believes might reasonably be related to participation in this study. The investigator should notify the study sponsor of any death or adverse event occurring at any time after a subject has discontinued or terminated study participation that may reasonably be related to this study. The sponsor should also be notified if the investigator should become aware of cancer development or a congenital anomaly in a subsequently conceived offspring of a subject that has participated in this study.

Hospitalization, Prolonged Hospitalization or Surgery

Any adverse event that results in hospitalization or prolonged hospitalization should be documented and reported as a serious adverse event unless specifically instructed otherwise in

CONFIDENTIAL

This document is confidential and the property of the Duke University.

this protocol. Any condition responsible for surgery should be documented as an adverse event if the condition meets the adverse event criteria.

Neither the condition, hospitalization, prolonged hospitalization, nor surgery is reported as an adverse event in the following circumstances:

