8.4 Recording of Adverse Events

At each contact with the subject, the investigator will seek information on adverse events by specific questioning and, as appropriate, by examination. Information on all adverse events will be recorded immediately in the medical record and noted in our REDCAP database. All clearly related signs, symptoms, and abnormal diagnostic procedures results should be recorded in the source document.

All adverse events occurring during the study period must be recorded. Each event's clinical course should be followed until resolution, stabilization, or until it has been determined that the study treatment or participation is not the cause. Serious adverse events that are still ongoing at the end of the study period must be followed to determine the outcome. Any serious adverse event that occurs after the study period and is considered to be possibly related to the study treatment or study participation should be recorded and reported immediately.

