Data will be captured in a RedCap© database. The database will be reviewed and discussed before database closure and closed only after resolving all remaining queries. An audit trail will be kept of all subsequent changes to the data. Only Key personnel will have access to the database.

10.5 *Records Retention*

As required by law and to enable evaluations and audits from regulatory authorities, the investigator agrees to keep records, including the identity of all participating subject's (i.e., sufficient information to link records to identify), all original signed informed consent forms, copies of all CRFs, other source documents, and detailed descriptions of treatment disposition

11 Study Monitoring, Auditing, and Inspecting

11.1 *Study Monitoring Plan*

This clinical research study will be monitored internally by the sponsor and monitored institutionally by the CQMP. In terms of the internal review, the sponsor will continuously

CONFIDENTIAL

This document is confidential and the property of the Duke University.

monitor and tabulate adverse events. Appropriate reporting to the Duke University Medical Center IRB will be made. If unexpected frequencies of events occur, action appropriate to the nature and frequency of these adverse events will be taken depending on their nature. This may require a protocol amendment, medication change, or potential closure of the study. The sponsor of this study will also continuously monitor the conduct, data, and safety of this study to ensure that:

- Stopping rules are met;
- The risk/benefit ratio is not altered to the detriment of the subjects;
- Appropriate internal monitoring of AEs and outcomes is done;
- Over-accrual does not occur;
- Under accrual is addressed with appropriate amendments or actions;
- Data are being appropriately collected in a reasonably timely manner

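### Section 8.2's abnormal-lab criterion is circular for lab tests, so a trivial new lab deviation counts as an adverse event whatever its clinical significance

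*Combined protocol and SAP*

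**What the plan says.** Section 8.2 (Adverse Event) opens with a general definition: an adverse event "is any symptom, sign, illness, or experience that develops or worsens in severity during the study". It then adds a sentence on test results, "Abnormal results of diagnostic procedures are considered to be adverse events if the abnormality" meets a condition in a list of six. In order, these are study withdrawal, a link to a serious adverse event, a link to signs or symptoms, "is associated with Abnormal lab values", extra treatment or testing, and "is considered by the investigator to be of clinical significance". No conjunction joins the items; the natural reading is that any one is enough. Neither 8.2 nor any other section defines an abnormal lab value or exempts one that is clinically unimportant.

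The reporting window in 8.2 opens at signed consent. Section 8.4 states: "All adverse events occurring during the study period must be recorded". It also requires each event to be followed until it resolves, stabilizes or is shown not to be caused by the study. Section 11.1 has the sponsor tabulate adverse events continuously and says: "If unexpected frequencies of events occur, action appropriate to the nature and frequency of these adverse events will be taken". Closing the study is among the possible actions.

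On lab testing, 4.3 says "relevant labs will be ordered as indicated by the pulmonary physician". The schedule in 6.2 marks labs at both V0 and V1. Section 6.2.2 lists them at V0, and 6.2.3 does not list them at V1.

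**The concern.** Five of the six criteria pick out abnormalities that matter: they had a consequence, came with symptoms or an SAE, or were judged important. The lab criterion asks only whether the abnormality goes with an abnormal lab value, and an abnormal lab result always does. A slightly out-of-range value that is new at V1, without symptoms, treatment, further testing or clinical importance, therefore qualifies.

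At stake is what the safety count means. Section 7.2 plans no safety analysis and 8.7 sets no stopping rules, so the 11.1 tabulation is the only frequency-based safety review described. In a study of 23 subjects, even a modest number of incidental lab deviations changes how that table reads beside the effects that 1.3.1 anticipates, such as dizziness, tingling, nausea or a contrast reaction. Each deviation also carries the follow-up duty in 8.4.

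**Working it through.** The plan states no figure that depends on this rule, so there is nothing to reproduce. The check has two parts.

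**1. Logic of the list.** Treat the six criteria as alternatives, so that one true criterion makes the result an adverse event.

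- *Lab result.* The lab criterion is always true. The other five can be true or false in 2^5 = 32 ways, and in 0 of 32 is the result not an adverse event. Setting clinical significance to true or false changes the answer in 0 of the 2^4 = 16 combinations of the remaining four.
- *Any diagnostic result, with the lab criterion free to be true or false.* Clinical significance decides in 1 of 32 combinations, namely when the other five are all false. An isolated CT, MRI, PFT or 6MWT abnormality with no related abnormal lab is such a case.
- *Lab result with the lab criterion deleted.* Five criteria remain. Clinical significance now decides in 1 of 16 combinations, when the other four are all false. That is the trivial deviation the list should be able to leave out.

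**2. Possible size.** From the documents: 23 subjects (3.1), of whom 13 are recruited for continuing respiratory symptoms (section 2), and two visits at which the schedule marks labs. Assumed, because the documents do not say: m = 5, 10 or 20 analytes per draw, independent of each other, each with a 5% chance of being out of range when nothing is wrong.

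- Chance that a subject has at least one out-of-range value per draw = 1 − 0.95^m.
- Expected out-of-range values = subjects × visits × m × 0.05.

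| | m = 5 | m = 10 | m = 20 |
|---|---|---|---|
| At least one per subject per draw | 22.6% | 40.1% | 64.2% |
| 23 subjects, two visits (46 × m × 0.05) | 11.5 | 23 | 46 |
| 23 subjects, one visit (23 × m × 0.05) | 5.75 | 11.5 | 23 |
| 13 subjects, two visits (26 × m × 0.05) | 6.5 | 13 | 26 |

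The 23-subject, two-visit row is a ceiling for each panel size. It assumes that everyone is tested twice and that every out-of-range value counts as new or worse. Labs drawn only as indicated, no labs at V1, V0 labs taken before consent, or stable pre-existing values would all lower it, possibly to near zero.

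**The case against.** **Labs may not be diagnostic procedures.** The documents do not say outright that they are. On the other reading, the criterion covers a non-lab abnormality accompanied by abnormal labs and is not circular. However, 12.1 gives labs, PFT and 6MWT together as examples of standard clinical procedures, so the reading that includes labs is the more natural one. A text open to both readings still needs repair.

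**The opening definition limits the rule.** A reader might infer that every out-of-range lab counts, including a chronic value present at V0 and again at V1. The develops-or-worsens condition plausibly excludes stable values. The test-result sentence does not repeat it, so the text is ambiguous, but the wider reading is not established. A trivial deviation that is new during the study remains caught either way.

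**Clinical significance still matters elsewhere.** A reader might infer that this criterion is void throughout. It is not: it still decides isolated imaging, PFT and 6MWT abnormalities.

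**Study outcomes.** A reader might also infer that an expected xenon MRI finding becomes an adverse event whenever some lab is out of range. The criterion requires association, not mere coexistence, and in a dyspneic subject the signs-or-symptoms criterion may already apply. That case does not demonstrate this defect.

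**Consequences are limited.** Section 11.1 weighs the nature of events as well as their frequency, and the schedule footnotes have a medical professional note xenon-related symptoms during the session. Over-inclusive recording also errs toward capture. All of this stands, so a claim that the table would be mostly noise is not supported.

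**Conclusion.** The point holds for lab tests only. Read as the text most naturally reads, section 8.2 makes any out-of-range lab that develops or worsens during the study an adverse event regardless of importance, and nothing elsewhere in the document corrects this. The number of such events cannot be derived from the documents. It runs from near zero to a ceiling of about 12 to 46, and the ceiling rests on the assumed panel of 5 to 20 independent analytes, the 5% rate and complete testing of 23 subjects at two visits. The effect falls on adverse-event recording, follow-up and tabulation. The imaging comparisons and the sample size in 7.1 do not depend on it. This is a drafting defect worth correcting, not evidence that the safety data would be unusable.

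**What to change.** In 8.2:

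- Delete the abnormal-lab criterion, or restrict it to lab abnormalities that the investigator judges clinically significant. Deletion is cleaner, because the restricted form repeats the last criterion.
- State that the develops-or-worsens condition in the opening sentence also governs the sentence on diagnostic results.
- State that any one of the remaining criteria is enough.

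Do not add a requirement that a result be new or worse than the subject's V0 value, and do not carve out study outcomes. A V0 result has no earlier V0 value to be compared with, so that wording would shut out V0 findings that are clinically significant or lead to further tests. Without it, the remaining criteria can still capture them.

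The cost is one deleted or qualified line and two clarifying statements, with no change to visits or data collection. The small downside is that some asymptomatic, untreated lab deviations would no longer be listed as adverse events.

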8.3 Life-Threatening Conditions

The cause of death of a subject in a study within 30 days of the end of the study, whether or not the event is expected or associated with the investigation, is considered a serious adverse event.

8.4 Recording of Adverse Events

At each contact with the subject, the investigator will seek information on adverse events by specific questioning and, as appropriate, by examination. Information on all adverse events will be recorded immediately in the medical record and noted in our REDCAP database. All clearly related signs, symptoms, and abnormal diagnostic procedures results should be recorded in the source document.

All adverse events occurring during the study period must be recorded. Each event's clinical course should be followed until resolution, stabilization, or until it has been determined that the study treatment or participation is not the cause. Serious adverse events that are still ongoing at the end of the study period must be followed to determine the outcome. Any serious adverse event that occurs after the study period and is considered to be possibly related to the study treatment or study participation should be recorded and reported immediately.

8.5 Study Closure

Following the completion of the studies, the sponsor will be responsible for ensuring the following activities:

- Data clarification and resolution
- Review of Site study records for completeness

8.6 *IRB Notification by Investigator*

Reports of all serious adverse events (including follow-up information) must be submitted to the IRB within ten working days. Copies of each report and documentation of IRB notification and receipt will be kept in the Clinical Investigator's binder.

CONFIDENTIAL

This document is confidential and the property of the Duke University.

8.7 Stopping Rules

No stopping rules are needed for this study. If patients want to withdraw. They can at any time.

8.8 Termination Criteria

Premature termination of these clinical trials may occur because of a regulatory authority decision, a change in opinion of the IRB, or the FDA's discretion. DUMC also reserves the right to discontinue the trial before inclusion of the intended number of subjects, but intends only to exercise this right for valid scientific or administrative reasons.

8.9 CQMP Monitoring

The Duke School of Medicine Clinical quality management program (CQMP) may conduct confidential audits to evaluate compliance with the protocols and GCP principles. The PI agrees to allow the CQMP reviewer direct access to all relevant documents and allocate his/her time and the time of the study team to the CQMP reviewer to discuss findings and any relevant issues. CQMP audits are designed to protect the rights and well-being of human research subjects.

8.10 Consent Process

The Duke IRB must approve the informed consent form and comply with ICH, GCP, local regulatory requirements, and federal laws. The investigator must ensure that each trial subject is fully informed about the trial's nature and objectives and possible risks associated with participation.

The investigator will obtain written informed consent from each subject before any study-specific activity is performed. The IRB must prospectively approve the informed consent form used in this trial, and any changes made during the trial before use. Additionally, the FDA will be notified of any changes before implementation as appropriate. The subject must sign this consent form, and the investigator-designated research professional obtaining the consent. The investigator will retain a copy of each subject's signed consent form.

9 Subject's Capacity to Give Legally Effective Consent

Subjects without the capacity to give consent will not be recruited into this study.

10 Data Handling and Record Keeping

10.1 Data Handling

At each contact with the subject, the investigator will seek information on adverse events by specific questioning and, as appropriate, by examination. Information on all adverse events will be recorded REDCAP database.

10.2 Source Documents

Source data is all information, original records of clinical findings, observations, or other activities in a clinical trial necessary to reconstruct and evaluate the trial. Source data are contained in source documents Examples of these original documents and data records include hospital records, clinical and office charts, laboratory notes, memoranda, subjects' diaries or evaluation checklists, pharmacy

CONFIDENTIAL

This document is confidential and the property of the Duke University.

dispensing records, recorded data from automated instruments, copies or transcriptions certified after verification as being accurate and complete, microfiches, photographic negatives, microfilm or magnetic media, x-rays, subject files, and records kept at the pharmacy, at the laboratories, and at medico-technical departments involved in the clinical trial.

10.3 *Case Report Forms*

As used in this protocol, the term CRF should be understood to refer to either a paper form or an electronic data record or both, depending on the data collection method used in this trial. A CRF is required and should be completed for each included subject. The completed original CRFs are the sole property of Duke. They should not be made available in any form to third parties, except for authorized representatives of Duke or appropriate regulatory authorities, without written permission from Duke.

It is the investigator's responsibility to ensure completion and to review and approve all CRFs. CRFs must be electronically signed by the investigator or by an authorized staff member. These signatures serve to attest that the information contained on the CRFs is true. At all times, the investigator has final, personal responsibility for the accuracy and authenticity of all clinical and laboratory data entered on the CRFs.

All consent and case report forms will be stored in a locked filing cabinet in the study coordinator or principal investigator's office. Any other digital data (images, image analysis) will be associated only with the subject identification number and the date and time of the ¹²⁹Xe MRI. Image data will be retrieved and analyzed only by study personnel. Data will be captured in a RedCap database. After all, manuscripts have been published, the key to the code will be destroyed.

10.4 *RedCap*

Data will be captured in a RedCap© database. The database will be reviewed and discussed before database closure and closed only after resolving all remaining queries. An audit trail will be kept of all subsequent changes to the data. Only Key personnel will have access to the database.

10.5 *Records Retention*

As required by law and to enable evaluations and audits from regulatory authorities, the investigator agrees to keep records, including the identity of all participating subject's (i.e., sufficient information to link records to identify), all original signed informed consent forms, copies of all CRFs, other source documents, and detailed descriptions of treatment disposition

11 Study Monitoring, Auditing, and Inspecting

11.1 *Study Monitoring Plan*

This clinical research study will be monitored internally by the sponsor and monitored institutionally by the CQMP. In terms of the internal review, the sponsor will continuously

CONFIDENTIAL

This document is confidential and the property of the Duke University.

monitor and tabulate adverse events. Appropriate reporting to the Duke University Medical Center IRB will be made. If unexpected frequencies of events occur, action appropriate to the nature and frequency of these adverse events will be taken depending on their nature. This may require a protocol amendment, medication change, or potential closure of the study. The sponsor of this study will also continuously monitor the conduct, data, and safety of this study to ensure that:

- Stopping rules are met;
- The risk/benefit ratio is not altered to the detriment of the subjects;
- Appropriate internal monitoring of AEs and outcomes is done;
- Over-accrual does not occur;
- Under accrual is addressed with appropriate amendments or actions;
- Data are being appropriately collected in a reasonably timely manner

